PDL1 – Programmed Cell Death Ligand 1

PFS - Progression Free Survival

PI3K - Phosphoinositide 3-Kinase

PJP – Pneumocystis jiroveci Pneumonia

PR – Partial Response

RECIST - Response Evaluation Criteria in Solid Tumors

RP2D – Recommended Phase 2 Dose

SAE – Serious Adverse Event

SD – Stable Disease

SJS – Stevens-Johnson Syndrome

TEN – Toxic Epidermal Necrolysis

TIA – Transient Ischemic Attack

TME - Tumor Microenvironment

T-vec - talimogene laherparepvec

ULN – Upper Limit of Normal

UPMC – University of Pittsburgh Medical Center

VZV – Varicella Zoster Virus

WCBP – Women of Child Bearing Age

IRB – Institutional Review Board

ii. Protocol Summary

[figure not shown]
Title	A Phase I/II Study of PI3K γ δ inhibitor Duvelisib in Combination with Nivolumab in Patients with Advanced Unresectable Melanoma who have Progressed on Anti-PD1 Therapy
Short Title	PI3 γ δ inhibition in PD1 Refractory Melanoma
Protocol Number	20-155
Phase	Phase I/II
Methodology	Single-arm, open label phase I/II study
Study Duration	We expect to enroll patients over 18 months and complete data analysis by 36 months.
Study Center(s)	UPMC Hillman Cancer Center
Objectives	For the Phase I portion, the primary objective is to determine the recommended phase II dose of duvelisib when combined with nivolumab using dose-limiting toxicity and immunologic parameters, and the secondary objectives are to assess early and late toxicities and the anti-tumor effect of combination therapy. The primary objective for the phase II cohort is to evaluate the anti-tumor effect of the combination of anti-PD1 therapy and duvelisib by comparing disease change using RECIST v1.1 criteria. Our secondary objectives are to assess 1) potential clinical benefit of combination therapy, 2) duration of response, 3) progression-free survival, 4) overall survival, and 5) safety measured by adverse events graded by CTCAE v5.0. A number of exploratory objectives will also be pursued including laboratory correlates.
Number of Subjects	42

Main Inclusion and Exclusion Criteria	
Inclusion criteria: Men and women 18 years of age or older with unresectable stage III or stage IV melanoma by AJCC 8th edition who have progressed on anti-PD1 therapy after a minimum of 12 weeks of therapy.
 
Exclusion criteria: Patients with known or suspected symptomatic or progressive CNS metastases; patients with treated CNS disease who are stable on repeat imaging at 2-4 weeks post SRS and neurologically stable are allowed. Patients with active autoimmune disease requiring treatment and patients with uveal or mucosal melanoma are not eligible. Patients with uncontrolled cardiovascular, pulmonary, and certain infectious disease are also excluded.

Investigational Product	
Duvelisib is an oral medication that will be administered in doses from 15mg once a day to 25mg BID for dose finding studies.
 
Nivolumab is supplied as a 240mg/24 mL formulation to be administered as an IV infusion at 240mg every 2 weeks, and if tolerated, potentially changed to 480mg once every 4 weeks.

Duration of administration	Both duvelisib and nivolumab will be administered in 4-week cycles until progression of disease, unacceptable toxicity, or 1 year, whichever is longer.
Reference therapy	For patients who have progressed on immunotherapy and targeted agents, there is no current standard of care ¹ and clinical trials are the recommended option.
Correlative studies	Patients will have peripheral blood draw and tumor biopsy performed at baseline and after 12 weeks of treatment in both phases of the trial. For the phase I cohort, changes in immune cell populations, particularly CD8+ T cell proliferation, will be used to measure the immunomodulatory effect of increasing doses of duvelisib. Additional studies are planned to characterize T cell phenotype, function, and metabolism as well to evaluate expression of genes involved in autoimmunity and inflammation and to correlate with toxicity. Correlative studies will be used along with toxicity data to inform the phase II dose. Ideally, the dose chosen will have a potent anti-tumor immune profile such as high CD8+ T effector cells, low T regulatory cells, low myeloid-derived suppressor cells.
Statistical Methodology	For the Phase I study, a modified 3+3 dose finding design is used, with 6 patients at each of 3 dose levels of 15mg daily, 25mg daily and 25mg twice daily. For the Phase II expansion, the expected response rate for treatment of patients with anti-PD1 beyond progression is <14% ² . For this study to be clinically relevant a response rate of at least 20% is sought from the addition of duvelisib. Regimen efficacy will be monitored using a Bayesian method. The trial will be stopped for futility if the posterior probability of response rate is <5% or is >70%. Response rate, progression free survival and overall survival will be analyzed via Kaplan-Meier methods. For safety analyses, a Bayesian monitoring scheme will also be used to monitor the severe adverse event rate.

Safety Evaluations	Patients will be evaluated at clinic visits at least every 2-4 weeks for safety analyses. Blood work will also be tested at these visits to evaluate any adverse effects. For patients with toxicity or other clinical concerns, additional visits and imaging may be warranted at the discretion of the treating physicians and in consultation with a study investigator.
Data and Safety Monitoring Plan	The Data Safety Monitoring Board consists of investigators, regulatory staff, CRS management, clinical research coordinators, data managers and clinic staff, and these will meet regularly at least monthly to discuss trial concerns and study data. The DSMB includes individuals not involved in study design or implementation. Information to be reviewed includes serious adverse events, safety issues, recruitment, accrual, protocol deviations and unanticipated problems. The protocol and investigators will also comply with IRB policy for reporting risk to subjects.

iii. Study Design Schematic

A Phase I/II Study of PI3K γ δ inhibitor Duvelisib in Combination with Nivolumab in Patients with Advanced Unresectable Melanoma who have Progressed on Anti-PD1 Therapy

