4.4 Subject Withdrawal or Termination

4.4.1 Termination of Study Participation

In the absence of treatment delays due to adverse event(s), treatment may continue until one of the following criteria applies:

- Disease Progression
- Intercurrent illness that prevents further administration of treatment
- Unacceptable adverse event(s)
- Patient decides to withdraw from the study
- General or specific changes in the patient's condition render the patient unacceptable for further treatment in the judgement of the investigator
- Patient non-compliance
- Pregnancy
 - All WCBP will be instructed to contact the investigator immediately if they suspect pregnancy at any time during study participation
 - The investigator must immediately notify the IRB in the event of a confirmed pregnancy in a patient participating in the study
- Termination of the study by sponsor
- Loss of access to one or both investigational agents
- The maximum planned duration treatment of 12 months has been completed.

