6.7 Safety Evaluations

Will be conducted according to the table below.

Table 6.7.1: Schedule of Study Procedures

Study Stage	Screening	Intervention									Safety Follow-up
Visit Number		1	2	3	4-6	7	8-9	10	11-15	16+	
Study Days (+/- 1 week) For cycles 1-4, visits every 14days, then every 28 days	-28 to 0	1-14	15-28	29-42	43-	85-98	99-126-168	169-196	197-364	365+	
Cycle Number		C1D1 and 15	C2D1 and 15	C3D1 and 15	C4-6 Day 1 and C4D15	C7D1	C8-9D1	C10D1	C11-15D1	C16+D1	
Informed Consent/Assent	X										
Review Inclusion/Exclusion Criteria	X										
Demographics/Medical History	X										
Physical Examination	X	X	X	X	X	X	X	X	X	X	
Vital Signs: BP, HR, RR, Temp O2	X	X	X	X	X	X	X	X	X	X	
Height and BMI	X										
Weight	X	X	X	X	X	X	X	X	X	X	
Pregnancy Test	X										
Assess contraceptive use	X	X	X	X	X	X	X	X	X	X	
EKG	X										
Prior/Concomitant Medications – including PJP and VZV prophylaxis	X	X	X	X	X	X	X	X	X	X	
Laboratory Evaluation	X	X	X	X	X	X	X	X	X	X	
Peripheral blood for correlates (week 0, 4*, 12, at progression) *For phase I		X	X		X Cycle 4 only						
Diagnostic imaging (every 12 weeks +/- 7 days)	X				X		X		X		
Biopsy for correlates (baseline, 12 weeks +/- 2 weeks)		X			X Cycle 4 only						
Dispense Investigational Product (IP)		X	X	X	X	X	X	X	X		
IP Compliance		X	X	X	X	X	X	X	X		
Adverse Events and Unanticipated Problems Assessment		X	X	X	X	X	X	X	X	X	

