	Mild/moderate diarrhea (Grade 1-2, up to 6 stools per day over baseline) and unresponsive to antidiarrheal agents	
Duvelisib
 
 - Withhold duvelisib until resolved - Initiate supportive therapy with systemic steroids - Monitor at least weekly until resolved - Resume at a reduced dose - Gastroenterology consultation, recommend endoscopy and biopsy 
Nivolumab
 
 - Withhold nivolumab until resolved - Resume at same dose - Support with systemic steroids, gastroenterology consultation, recommend endoscopy and biopsy
	Abdominal pain, stool with mucus or blood, change in bowel habits, peritoneal signs, OR Severe diarrhea (Grade 3, >6 stools per day over baseline)	
Duvelisib
 
 - Withhold duvelisib until resolved - Initiate supportive therapy with enteric acting steroids (e.g., budesonide) or systemic steroids - Monitor at least weekly until resolved - Resume at a reduced dose

Toxicity	Adverse Reaction Grade	Recommended Management
		
 - For recurrent Grade 3 diarrhea or recurrent colitis of any grade, discontinue duvelisib 
Nivolumab
 
 - Withhold nivolumab until resolved - Resume at same dose - Systemic steroids, gastroenterology consultation and biopsy - If no improvement in 3-5 days, consider addition of infliximab
	Life-threatening, grade 4	
Duvelisib
 
 - Discontinue duvelisib 
Nivolumab
 
 - Permanently discontinue nivolumab - Systemic steroids, gastroenterology consultation and biopsy - If no improvement in 3-5 days, consider addition of infliximab
Cutaneous reactions	Grade 1	
Duvelisib
 
 - No change in dose - Initiate supportive care with emollients, antihistamines (for pruritus), or topical steroids - Monitor closely 
Nivolumab
 
 - Continue nivolumab - Support with topical emollients and/or mild-moderate potency topical corticosteroids
	Grade 2	
Duvelisib
 
 - Consider holding duvelisib, restart at same dose - Initiate supportive care with emollients, antihistamines (for pruritus), or topical steroids - Monitor closely 
Nivolumab
 
 - Consider holding nivolumab until resolved - Resume at same dose once improved to grade 1

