11.4 Pneumonitis

Serious cases of pneumonitis occurred with duvelisib. Median time to onset of any grade was 4 months with the majority of cases occurring prior to 9 months and with a mean duration of event of 1 month. Subjects should report new cough or shortness of breath. Patients who have pulmonary signs and symptoms such as cough, dyspnea, hypoxia, radiologic changes, or decline of >5% in oxygen saturation should have duvelisib held and be evaluated. Infectious etiologies should be treated as above. Systemic steroids should be considered. For moderate disease, reduced duvelisib doses can be considered. If non-infectious pneumonitis recurs or does not respond to steroid therapy, discontinue duvelisib. For severe or life-threatening pulmonary disease, duvelisib should be permanently discontinued.

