14.2. Phase II Portion of the Study

The study primary endpoint will be analyzed once the last patient on treatment is on study for 18 weeks.

14.2.1. Study Populations:

Safety population: patients who received any amount of the study regimen.

[figure not shown]
Efficacy population: patients who received at least one cycle of the treatment and at least one efficacy evaluation.

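### The synopsis makes one year a minimum treatment duration for both drugs; section 4.4.1 makes 12 months the maximum and stops at the first qualifying event

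*Combined protocol and SAP*

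**What the plan says.** The synopsis row on duration of administration covers both drugs, which are given in 4-week cycles "until progression of disease, unacceptable toxicity, or 1 year, whichever is longer".

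Section 4.4.1, Termination of Study Participation, says that "treatment may continue until one of the following criteria applies". The list that follows includes disease progression, unacceptable adverse events, and this item: "The maximum planned duration treatment of 12 months has been completed". (Two sections carry the number 4.4.1. The other, on duration of follow-up and retreatment, is not the one meant here.)

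The toxicity sections also stop treatment without reference to elapsed time. Table 7.6 has "Permanently discontinue nivolumab" for grade 4 diarrhea or colitis, among other events. Section 11.4 says: "For severe or life-threatening pulmonary disease, duvelisib should be permanently discontinued".

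**The concern.** The duration of treatment is a dosing instruction, and two current parts of the protocol state it in opposite directions. A reader who works from the synopsis could keep a patient without progression on both drugs past month 12. A reader who works from section 4.4.1 would stop, and would record the other conduct as a deviation.

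The synopsis wording also sits badly with the safety rules. Sections 11.1 to 11.4 give median onset times of 3 months for infection, 4 months for diarrhea or colitis, 3 months for cutaneous reactions and 4 months for pneumonitis. All fall inside the year that the synopsis literally treats as a minimum.

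The end of treatment also fixes other windows. Adverse events are collected to 100 days after treatment ends (sections 3.2.2, 8.2.2 and 8.4). Section 14.2.3.2 gives 18 months as an example time point for PFS and OS. Under section 4.4.1 patients are off study treatment by then; under the synopsis some could still be on it.

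**Working it through.** The plan has no figure to reproduce, so this is a comparison of rules.

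Let P be the month of progression, T the month of unacceptable toxicity, and 12 the time limit.

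- Synopsis, read literally: stop = max(P, T, 12).
- Synopsis, milder reading (the first of progression and toxicity, but not before one year): stop = max(min(P, T), 12).
- Section 4.4.1, using only these three criteria: stop = min(P, T, 12). Its other criteria can only bring the stop forward.

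| Patient | Synopsis, either reading | Section 4.4.1 |
|---|---|---|
| Progression at month 3 | month 12 or later | month 3 |
| Unacceptable toxicity at month 2 | month 12 or later | month 2 |
| Neither by month 12 | continues past month 12 | month 12 |

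The rules differ in all three cases. Under both readings of the synopsis the stop is never earlier than month 12; under section 4.4.1 it is never later. In four-week cycles the cap is 364 / 28 = 13 cycles.

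**Which text is intended.** Section 4.4.1 calls 12 months a maximum, which cannot be squared with a floor. Table 7.6 and section 11.4 confirm that toxicity stops treatment at any time, but say nothing about the 12-month cap. On the cap, the schedule in Table 6.7.1 gives limited support. As extracted, physical examination has 10 marks (screening plus 9 on-study columns, the last at day 365+). Drug dispensing has 8, the last at days 197-364, with none at day 365+. Column alignment is inferred, and the day 365+ column carries a cycle label, so this is corroboration only.

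**Reach into the statistics.** Response is first assessed at 12 weeks (section 3.2.1) and acute DLTs are counted to day 28 (section 8.1). The sample size and the futility and toxicity boundaries in section 14 do not use treatment duration. The timing of the primary analysis is set by section 14.2: "The study primary endpoint will be analyzed once the last patient on treatment is on study for 18 weeks".

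**The case against.** The strongest reply is that this is an editorial slip. The body has an explicit termination list and toxicity-specific discontinuation rules, and nobody would dose through unacceptable toxicity because of one synopsis phrase. Much of that is fair. The toxicity and progression conflicts are largely theoretical, and the real dispute narrows to the patient still on treatment at month 12. But the available text states no rule that the body prevails over the synopsis. The summary of changes lists two edits to this same synopsis table and none to the duration row, so the wording is current.

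A second objection is that the schedule table is weak evidence for the cap. That stands, and the conclusion does not depend on it: the synopsis and section 4.4.1 suffice.

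A third is that the primary endpoint is not wholly insulated. Response is the best response up to progression (sections 12.3.3 and 14.2.3.1), with scans every 12 weeks. Enrollment over 18 months is about 78 weeks (18/12 x 52). Adding 18 weeks gives 96, so the earliest patients could have scans at weeks 60, 72, 84 and 96, after month 12 and by the primary analysis. The observed rate would change only if the choice of rule altered whether a patient first responded that late. That is a remote route, but not an impossible one. The endpoint definition, sample size and boundaries are untouched.

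**Conclusion.** The concern holds. The synopsis states a floor of one year and section 4.4.1, Termination of Study Participation, states a ceiling of 12 months with a stop at the earliest event. The synopsis is the text that is wrong.

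The practical effect is limited to patients still on both drugs at month 12, out of at most 42. Their number cannot be estimated from the documents. This assumes that investigators follow the toxicity and progression stops in the body; if the synopsis were followed literally, the affected group would be wider. The correction should be made because it concerns dosing and safety wording. It gives no reason to revisit the design.

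**What to change.** In the synopsis row on duration of administration, change the closing qualifier to *whichever occurs first*, so that treatment ends at progression, unacceptable toxicity or 12 months. Leave section 4.4.1, Termination of Study Participation, as it stands.

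The cost is one phrase in the next amendment. Design, sample size, monitoring boundaries and analysis do not change.

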14.2.2. Study Design and Interim Analysis

The primary objective of this study is to evaluate the overall response rate to the combination of anti-PD1 therapy and duvelisib. We would consider the combination futile and not worth further study if the response rate is 5% or lower. We will monitor the efficacy of the regimen using a Bayesian method. We will consider the trial futile and propose stopping if the posterior probability that response rate is <5% given the observed data is >70%. A non-informative prior of Beta (0.5, 0.5) is used for the true response rate and the cohort size is set to be 5. The futility early stopping boundaries are given in the following table:

# Patients (inclusive)	# Responses (inclusive) are considered futile	Actions
5	Never stop with this many patients	
10	Never stop with this many patients	
15	0	Early stopping
20	0	Early stopping
25	0	Early stopping

Therefore, if none of the first 15 patients responds to the combination, the study will be stopped early for futility. Otherwise, the study will continue to recruit all 30 patients. By the end of the study, we will consider the study combination effective and worth further study if the posterior probability that the response rate is $>5\%$ given the observed data is 90% or higher (in our case, if we observe >3 responses in 30 evaluable patients). The following figure demonstrated the simulation results of the operating characteristics of our study design, under the assumption of various true response rates. As shown, when the response rate is 5% or lower, the probability of early stop is higher (>0.46) and probability of declaring efficacy (i.e. “type I error”) is low (<0.06). When the response rate is 20% or higher, the probability of early stopping is less than 3.5% and the probability of declaring efficacy (i.e. “power”) is over 86%.

The simulation is performed using the web tool for Bayesian Efficacy Monitoring Via Posterior Probability (<http://www.trialdesign.org/one-page-shell.html#BEMPO>).

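### The final success rule tests against an unexplained 5% response rate, not the rate of up to 14% expected from anti-PD1 alone, so 4 of 30 cannot show that duvelisib adds anything

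*Combined protocol and SAP*

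**What the plan says.** The Protocol Summary (section ii, Statistical Methodology) gives two reference points for phase II. Without duvelisib, "the expected response rate for treatment of patients with anti-PD1 beyond progression is <14" per cent, which is an upper bound with no point estimate. With it, "For this study to be clinically relevant a response rate of at least 20% is sought from the addition of duvelisib".

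Section 14.2.2 works from a third figure: "We would consider the combination futile and not worth further study if the response rate is 5% or lower". The prior and monitoring are stated clearly: "A non-informative prior of Beta (0.5, 0.5) is used for the true response rate and the cohort size is set to be 5". Interim futility is to "propose stopping if the posterior probability that response rate is <5% given the observed data is >70" per cent, which in practice means that "if none of the first 15 patients responds to the combination, the study will be stopped early for futility". At the end, "we will consider the study combination effective and worth further study if the posterior probability that the response rate is" above 5% "given the observed data is 90% or higher", stated as more than 3 responses in 30 evaluable patients.

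The text of 14.2.2 gives operating characteristics at 5% or lower (early stopping above 0.46, declaring efficacy below 0.06) and at 20% or higher (early stopping below 3.5%, declaring efficacy over 86%). It also refers to a figure covering various true response rates; that figure is not reproduced in the text available for review. Section 14.2.3.1 adds the observed response rate with exact 95% limits. Section 14 nowhere mentions the 14% figure and gives no reason for choosing 5%.

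**The concern.** Every patient receives nivolumab with duvelisib and there is no control arm. If duvelisib contributed nothing, the trial would simply observe the response rate of continued anti-PD1. The reference rate in the success rule is therefore what separates an active combination from anti-PD1 doing what it would have done anyway. The protocol puts that rate somewhere below 14%. The rule tests against 5%, and nothing says that 5% is the rate expected without duvelisib.

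The lowest winning result, 4 of 30, is 13.3%. That lies inside the range the protocol allows for anti-PD1 alone, yet the plan would describe it as effective. Section 1.0 states the hypothesis that duvelisib helps overcome anti-PD1 resistance, and the summary speaks of the response rate sought from its addition. A reader of a positive result is likely to take it as support for that hypothesis, and the stated error rate of under 6% does not protect that reading.

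**Working it through.** **Inputs.** From section 14.2.2: prior Beta(0.5, 0.5), n = 30, stop if 0 of the first 15 respond (the 0/20 and 0/25 boundaries are then redundant), success at 4 or more of 30, reference rate 5%. From the Protocol Summary: anti-PD1 alone below 14%, target at least 20%.

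**Formulas.** With x responses in n patients the posterior is Beta(0.5 + x, 0.5 + n − x). For a true rate p, the chance of declaring success is

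P(X₃₀ ≥ 4) − (1 − p)¹⁵ × P(X₁₅ ≥ 4),

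where the subtracted term removes trials that stop at 0/15 but would otherwise have had 4 or more responses among the last 15 patients.

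**Step 1: reproduce the plan.**
- With 0 responses, Pr(ORR <5%) is 0.537 (n=5), 0.695 (n=10), 0.789 (n=15), 0.851 (n=20) and 0.893 (n=25). The first to pass 0.70 is 0/15, as tabulated.
- Pr(ORR >5%) is 0.890 at 3/30 and 0.968 at 4/30, so the bar is 4/30 = 13.3%.
- At p = 5%: early stop 0.95¹⁵ = 0.463; success 0.0608 − 0.4633 × 0.0055 = 0.058. The plan says >0.46 and <0.06.
- At p = 20%: early stop 0.80¹⁵ = 0.0352; success 0.8773 − 0.0352 × 0.3518 = 0.865. The plan says <3.5% and >86%. The 0.0002 difference in early stopping is within simulation error.

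The arithmetic is right for a 5% reference.

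**Step 2: the same rule if duvelisib adds nothing.** The true rate is then the anti-PD1-alone rate, which the documents bound but do not state. It is treated here as an assumption and varied.

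| Assumed anti-PD1-alone rate | P(X₃₀ ≥ 4) | (1−p)¹⁵ | P(X₁₅ ≥ 4) | P(declare effective) |
|---|---|---|---|---|
| 5% | 0.0608 | 0.4633 | 0.0055 | 0.058 |
| 8% | 0.2158 | 0.2863 | 0.0273 | 0.208 |
| 10% | 0.3526 | 0.2059 | 0.0556 | 0.341 |
| 12% | 0.4929 | 0.1470 | 0.0959 | 0.479 |
| 14% (upper limit) | 0.6215 | 0.1041 | 0.1476 | 0.606 |

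**Step 3: what each final result says about the protocol's own figures.**

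| Responses of 30 | Pr(ORR >5%) | Pr(ORR >14%) | Pr(ORR >20%) |
|---|---|---|---|
| 4 | 0.968 | 0.484 | 0.183 |
| 5 | 0.993 | 0.682 | 0.338 |
| 6 | 0.999 | 0.831 | 0.519 |
| 7 | >0.999 | 0.923 | 0.689 |

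The exact 95% interval at 4/30 is 3.8% to 30.7%. The first result to reach 0.90 against 14% is 7/30 (23.3%).

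**Step 4: what a bar of 7/30 would cost if it replaced 4/30.** With the same futility rule, the chance of reaching 7/30 is 0.116 at a true 14% and 0.392 at a true 20%. An exact single-stage test of 14% against 20% with 80% power needs about 175 patients at one-sided 0.10, or about 239 at one-sided 0.05. Thirty patients cannot separate the two rates well.

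**The case against.** The strongest defence is that this is an early go/no-go screen. The primary objective and endpoint concern the activity of the combination, not the isolated effect of duvelisib. A low reference rate is an accepted way to discard inactive regimens, and 14.2.2 says openly that its error rate applies at 5% or lower. The exact 95% limits in 14.2.3.1 would show that 4/30 does not exclude 14%. All of that stands, and it is why the bar itself need not move.

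Several stronger readings are tempting and are not supported:

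- *The trial has a 61% false-positive rate.* The 14% is an upper bound, so 0.61 is the top of a range. The figure comes from a cited pooled analysis that cannot be checked here. This trial also sets no limit on time since anti-PD1 or on later therapies (section 4.1), so the rate without duvelisib in this population is unknown.
- *Success can be declared below the anti-PD1-alone rate.* The value 13.3% lies within the stated range; the documents do not show that it is below the true rate.
- *The plan ignores its 20% target.* It uses 20% as the design alternative, with power over 86%. A success bar below the alternative is normal in a single-arm design.
- *The plan conceals its behaviour between 5% and 20%.* The missing figure may show it.

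What the defence does not supply is a reason for 5% beside the protocol's own 14%, or a reason to call 4/30 effective rather than not inactive. Nor does the concern need the full 14%: at 8% the chance of a declaration is already 0.21, more than three times the stated limit of 0.06.

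**Conclusion.** The point holds as a mismatch between the reference rate and the wording of the conclusion; it is not an error of calculation. Section 14.2.2 tests against an unexplained 5% and does not use the anti-PD1-alone rate as its reference. If duvelisib adds nothing, the chance of declaring the combination effective runs from 0.058 to 0.61 as the anti-PD1-alone rate runs from 5% to 14%. The quoted limit of 0.06 applies only if that rate is about 5% or lower, which the documents do not claim. At the minimum winning result the posterior odds that the response rate exceeds 14% are about even (0.48).

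This rests on the stated prior, futility rule and 30 evaluable patients, and on taking the summary's bound as relevant to the enrolled population. It does not show that 30 patients or the 4/30 screen are wrong. It limits what a result of 4, 5 or 6 of 30 may be said to mean.

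**What to change.** Keep n=30, the futility rule and 4/30 as the go/no-go screen. In section 14.2.2:

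1. Give the reason for 5%, and replace the description of the combination as effective with: *response rate above 5%; worth further study*.
2. Report Pr(ORR >14%) and Pr(ORR ≥20%) beside the exact 95% interval.
3. Allow a statement that the result exceeds the rate expected from anti-PD1 alone only if Pr(ORR >14%) is at least 0.90, that is 7 or more of 30. State that this second criterion has about 0.39 power at a true 20% and is not the go/no-go rule.
4. If the figure does not already show it, state in the text the chance of meeting the 4/30 rule at a true 10% (0.34) and 14% (0.61).

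The cost is a few sentences and two posterior probabilities, with no extra patients and no change to enrolment. The downside is that 4 to 6 of 30 would support further study but not a claim that duvelisib adds to anti-PD1, and a regimen that truly reaches 20% would miss the second criterion about 61% of the time (1 − 0.39).
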